## 10.2 Sample Size Considerations

The primary endpoint is objective response rate (CR+PR) as defined earlier in the metastatic MCM population. ORR in the ALM populations will be exploratory. The response rate with current standard therapy is approximately 23-25%(65). Secondary clinical endpoints include, median PFS and OS, 6 month landmark PFS and 1 year landmark OS. Biomarker exploratory endpoints will include: 1) the relationship of CD8 T cell score at the invasive margin and tumor response for each malignancy and 2) the relationship with tumor mutational frequency using whole exome sequencing and response. Bioinformatic tools will be used in an attempt to identify recurring driver mutations in MCM (as well as ALM).

The sample size is based on the primary endpoint objective response rate (ORR). The null hypothesis that the ORR is at most 25% will be tested against a one-sided alternative. If the ORR is less than 25%, we will consider this therapy not worth pursuing. If it is more than 25%, the therapy is considered worth pursuing. With 39 patients, the study would have 90% power at a significance level of 10% if the true ORR is 45%. To take into consideration a potential non-evaluable or dropout rate of 20%, 49 patients with MCM (cohort A) will need to be enrolled into this study. The exact binomial calculation is used.

Given the less frequent occurrence of metastatic melanoma involving ALM subtypes, we will plan to enroll only 24 patients with ALM (cohort B). This should allow the accrual to both cohorts to finish at roughly the same time. Analysis of activity Cohorts B and the biomarker data will be primarily descriptive and exploratory.

Patients who enroll in this trial but do not receive the immune checkpoint inhibitor combination, or those for whom tissue is not submitted (see section 9.0) and therefore cannot be classified into a predictive factor group, will be deemed unevaluable for the primary endpoint of the study; available information on these patients will be described in the final report.

The overall accrual rate is anticipated to be 2-4 patients per month on each cohort, based on past experience among each institution in the Melanoma Research Foundation Breakthrough Consortium , resulting in expected accrual duration of about 20-24 months. The trial's primary analyses are planned to occur at 6 months after each patient has received the treatment.

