## 5.2 Duration of Therapy and Response Assessment

All patients will receive nivolumab administered IV combined with ipilimumab administered IV every 3 weeks for 4 treatment cycles per standard of care (Induction) then continue with nivolumab administered IV per standard of care until progression, intolerable toxicity, or a maximum of 48 doses, whichever comes first (Maintenance). Patients exhibiting complete response (CR) should continue nivolumab monotherapy at least 12 weeks beyond documentation of CR, if possible. Patients will be treated within participating sites within the MRFBC. Commercial drugs will be used in this protocol and will not be supplied by the study.

Patients will be evaluated for response at approximately 12 weeks following the initiation of treatment and then approximately every 12 weeks. Response will be evaluated by the study investigators using the Response Evaluation Criteria in Solid Tumors (RECIST) criteria ,v1.1. (See appendix C). Following completion of therapy, patients with evidence of SD, PR or CR will have CT scans every 3 months for 2 years, then every 6 months during year 3 and then yearly thereafter for years 4 and 5. Attention will be paid to the time of disease progression. Both responding and non-responding patients will be followed until death.

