## 10.3 Statistical Analysis for Correlative Studies

### 10.3.1 Best Overall Response

The proportion of patients achieving a response (best overall response; complete or partial response as per RECIST v1.1 criteria (outlined in appendix C) and exact binomial 95% CI will be calculated. Objective response rates (complete response + partial response) will be calculated separately for each cohort.

Among all enrolled patients, additional hypothesis-generating analyses will be undertaken to explore whether somatic mutational loads, difference in driver mutation profiles, level of pre-treatment CD8+ TIL and PD-L1 expressing cells at the invasive tumor margin, presence of tumor specific neoantigen, TCR clonality, gene expression profiles and enrichment of specific gut microbiota might be associated with responsiveness in order to further refine the optimal population for treatment with ipilimumab and nivolumab combination in MCM and ALM.

Categorical factors and continuous factors will be compared between responders and non-responders using Fisher's exact tests and two-sample Wilcoxon rank sum test respectively.

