## **Appendix D** **RECIST v1.1 Response Criteria**

Definitions of measurable, non-measurable, target and non-target lesions and objective response criteria based on the REVISED (January, 2009) RECIST 1.1 criteria. This Appendix is for reference only. The complete RECIST 1.1 criteria are found at: [www.recist.com](http://www.recist.com).

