#### 4.3 Evaluation of best overall response

The best overall response is the best response recorded from the start of the treatment until disease progression/recurrence (taking as reference for progressive disease the smallest measurements recorded since the treatment started). The patient's best response assignment will depend on the achievement of both measurement and confirmation criteria.

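### Does the undefined start of the 6 months to the primary analysis leave late responses unconfirmed?

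*Combined protocol and SAP*

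**What the plan says.** Section 10.2 sets the timing in one sentence: "The trial's primary analyses are planned to occur at 6 months after each patient has received the treatment". It plans for 39 evaluable mucosal melanoma patients, states that "49 patients with MCM (cohort A) will need to be enrolled into this study", and describes accrual as "resulting in expected accrual duration of about 20-24 months".

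Section 5.2 gives the scan schedule: "Patients will be evaluated for response at approximately 12 weeks following the initiation of treatment and then approximately every 12 weeks". Under the same section, treatment is four induction cycles three weeks apart, then nivolumab for up to 48 doses, so receipt of treatment has no single date. Section 10.3.2 times PFS and OS from treatment initiation; section 10.2 names no such origin for the primary analysis.

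Section 10.3.1 defines the endpoint as "best overall response; complete or partial response as per RECIST v1.1 criteria" and does not mention confirmation. Confirmation appears in two appendices:

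- Appendix D (4.3 and 5.1) calls for a repeat study at least 4 weeks later in a non-randomized trial with response as the primary endpoint. The appendix opens with "This Appendix is for reference only".
- Appendix F, a suggested schedule, asks in footnote a for a confirmatory scan 6 to 12 weeks after a response.

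Appendix D 4.3 sets no 6-month limit on the endpoint: "The best overall response is the best response recorded from the start of the treatment until disease progression/recurrence".

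**The concern.** If the clock starts at first dose, six months is about week 26. The week-24 scan feeds the primary endpoint, but a response first seen on it could not yet be confirmed for the last patients enrolled. Either those responses would be scored as non-responses, which costs power, or the confirmation requirement would be relaxed with the data in hand, which raises type I error. The trial is single-arm and investigator-assessed, and its test turns on one response: 14 of 39 rejects the null hypothesis and 13 of 39 does not. An open choice about which responses count therefore deserves a check.

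**Working it through.** **Inputs.** From section 10.2: null ORR 25%, alternative 45%, one-sided 10% level, 39 evaluable, 49 enrolled, accrual over 20 to 24 months. From section 5.2: scans at about weeks 12, 24 and 36, and induction doses at weeks 0, 3, 6 and 9. Confirmation intervals: at least 4 weeks (Appendix D 5.1), 6 to 12 weeks (Appendix F). One month = 365.25/12/7 = 4.348 weeks.

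**Step 1: reproduce the design.** The smallest r with P(X ≥ r | 39, 0.25) ≤ 0.10 is 14.

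- P(X ≥ 14 | 39, 0.25) = 0.0862, and P(X ≥ 13 | 39, 0.25) = 0.1545.
- Power = P(X ≥ 14 | 39, 0.45) = 0.9048.
- Enrolment = 39/0.8 = 48.75, so 49.

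The stated figures hold.

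**Step 2: where the analysis falls under each start point.** Six months = 6 × 4.348 = 26.1 weeks.

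- From first dose: week 26.1.
- From the fourth induction dose: 9 + 26.1 = week 35.1.
- From the end of the fourth cycle: 12 + 26.1 = week 38.1.

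A week-24 response is confirmable at 24 + 4 = 28, 24 + 6 = 30 or 24 + 12 = 36. Only the first-dose reading falls before all three. From the fourth dose, only the full 12-week interval is missed, by about a week. From the end of induction, none is missed. A week-12 response is confirmable by weeks 16 to 24 on every reading.

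**Step 3: patients short of follow-up on the first-dose reading.** Assume one calendar cut 6 months after the last patient's first dose, with later scans excluded. Number = gap in months × evaluable accrual rate, where the rate is 39/24 = 1.63 to 39/20 = 1.95 per month.

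| Confirmation | Gap (weeks) | Gap (months) | Evaluable patients |
|---|---|---|---|
| Week 28 | 1.9 | 0.44 | 0.7 to 0.9 |
| Week 30 | 3.9 | 0.90 | 1.5 to 1.8 |
| Week 36 | 9.9 | 2.28 | 3.7 to 4.4 |

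Section 10.2 also gives 2 to 4 patients per month per cohort. At 4 per month with 80% evaluable, the last row would reach 7.3. But that rate fills 49 places in 49/4 = 12.25 months, which does not fit the stated accrual duration.

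**Step 4: effect on the test.** These patients lack follow-up; they are not all misclassified. Let f be the share of responders first responding at week 24. The documents give no value, so assume 10 to 30%. Expected responses lost = k × 0.45 × f. Power is the exact probability of at least 14 responses with k patients at 0.45(1 − f) and 39 − k at 0.45.

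| k | f | Expected loss | Power |
|---|---|---|---|
| 1 | 10% | 0.05 | 0.9024 |
| 1 | 30% | 0.14 | 0.8975 |
| 4 | 10% | 0.18 | 0.8947 |
| 4 | 30% | 0.54 | 0.8729 |

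The fall from 0.9048 is 0.2 to 0.7 percentage points with one patient and 1.0 to 3.2 with four.

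If unconfirmed responses are counted instead, and add 1 to 3 points to a 25% ORR in these patients (assumption), type I error is 0.0868 to 0.0880 with one patient and 0.0886 to 0.0936 with four. All are below 0.10.

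**Step 5: would a 9-month cut help?** 9 × 4.348 = 39.1 weeks, which is 13.0 weeks later. A response first seen at week 36 is confirmable at week 40, 42 or 48, so it falls short by 0.9, 2.9 or 8.9 weeks. The corresponding gaps at six months are 1.9, 3.9 and 9.9 weeks. Any fixed cut shortly after a scan has this edge.

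**The case for a change.** The strongest reply is that the missing start point is a fact on any reading, and that the choice would be made by people who can see the responses. The decision boundary is sharp: p = 0.086 at 14 responses and 0.154 at 13. The wording also permits a harsher reading, in which every patient's response is frozen six months after that patient's own first dose. All 39 would then be exposed. On the same 10 to 30% assumption, power would be P(X ≥ 14 | 39, 0.405) = 0.771 down to P(X ≥ 14 | 39, 0.315) = 0.332. Counting unconfirmed responses would give a type I error of 0.112 at an ORR of 26% and 0.178 at 28%.

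Part of this stands. The start point is not stated, section 10.3.1 does not say whether ORR is confirmed, and the two appendices give different intervals.

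The freezing reading does not stand. Section 10.2 says when the analyses take place, not that scans beyond six months are discarded. Appendix D runs best response to progression, section 5.2 keeps patients on scheduled scans, and for all but the last patients enrolled the later scans would already be in hand at the analysis. Nor does sharpness at the boundary make a reversal likely. It requires a count at the boundary and also a late, unconfirmed response among the few patients concerned, which is why the power loss in step 4 is small.

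**Conclusion.** No change to the plan is called for. Section 10.2 leaves a detail open, and the rest of the document lets analysts fill it sensibly: best response has no six-month limit, scanning continues, Appendix F already asks for a confirmatory scan, and waiting for a pending one breaches no stated rule.

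The problem arises only if the six months run from first dose and later scans are also excluded, and the plan states neither. On that worst combination, with a single calendar cut and the stated accrual duration, about 1 to 4 evaluable patients are short of follow-up and the expected loss is about half a response at most. Power stays between 87.3 and 90.2% and type I error stays within 10%. The late-responder share (10 to 30%) and the added response rate (1 to 3 points) behind these figures are assumptions.

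A later fixed cut would be a trade-off, not a correction: it postpones the readout by 13 weeks and moves the same edge to the week-36 scan.

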## 10.3 Statistical Analysis for Correlative Studies

### 10.3.1 Best Overall Response

The proportion of patients achieving a response (best overall response; complete or partial response as per RECIST v1.1 criteria (outlined in appendix C) and exact binomial 95% CI will be calculated. Objective response rates (complete response + partial response) will be calculated separately for each cohort.

Among all enrolled patients, additional hypothesis-generating analyses will be undertaken to explore whether somatic mutational loads, difference in driver mutation profiles, level of pre-treatment CD8+ TIL and PD-L1 expressing cells at the invasive tumor margin, presence of tumor specific neoantigen, TCR clonality, gene expression profiles and enrichment of specific gut microbiota might be associated with responsiveness in order to further refine the optimal population for treatment with ipilimumab and nivolumab combination in MCM and ALM.

Categorical factors and continuous factors will be compared between responders and non-responders using Fisher's exact tests and two-sample Wilcoxon rank sum test respectively.

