### **1.7 Immunotherapy in Metastatic MCM and ALM**

Immunotherapy with HD-IL-2 produces durable benefit in 10% of patients with metastatic cutaneous melanoma. Little data is available about the value of HD IL-2 in patients with MCM and ALM. A multicenter, retrospective study in 2013 evaluating 33 patients with advanced MCM who were treated with ipilimumab found a treatment response rate roughly comparable to that seen in patients with cutaneous melanoma and a durable response rate of 6.7%(4.2-10.9%) (35). Another retrospective study of 71 subjects with advanced MCM who received ipilimumab as a part of European Expanded Access Program also demonstrated similar objective response rate of 12%, with a median progression-free survival of 4.3 months (95%CI:3.4-5.2)(36).

In a recent multi-institutional retrospective analysis of 60 patients with advanced acral and mucosal melanoma treated with anti-PD1 inhibitor monotherapy (nivolumab or pembrolizumab), including patients from published prospective trials, expanded access program and standard treatment (following pembrolizumab approval in 2014), with 77% of patients received prior ipilimumab treatment, objective response rate was 32%(15-54%) in ALM, and 23% (10-40%) in MCM respectively, comparable to the response rate in cutaneous melanoma. Half of patients (8/16) with objective response developed relapsed disease with median duration

of response of 12.9 months (95%CI: 2.1-15.9), and median progression-free survival of 3.9 months (unpublished MSKCC data; In Press)

Despite the potential treatment benefit, majority of patients with metastases from these rare variant melanomas either do not respond or only have only a transient response and therefore require additional or improved therapeutic options.

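### Section 10.3.1 tests markers against response across both diseases without stratifying by cohort, and disagrees with section 10.2 on CD8

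*Combined protocol and SAP*

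**What the plan says.** Section 10.3.1 treats cohort in two ways. For the response rate it is explicit: "Objective response rates (complete response + partial response) will be calculated separately for each cohort". The next paragraph turns to the markers and changes the population: "Among all enrolled patients, additional hypothesis-generating analyses will be undertaken to explore whether somatic mutational loads". The list goes on to driver profiles, CD8+ infiltrate, PD-L1, neoantigens, TCR clonality, expression profiles and gut microbiota. The method follows: "Categorical factors and continuous factors will be compared between responders and non-responders using Fisher's exact tests and two-sample Wilcoxon rank sum test respectively". No stratum, covariate or check of whether a marker acts differently in the two diseases is named.

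Section 10.2 words the two biomarker endpoints differently from each other. The first is "the relationship of CD8 T cell score at the invasive margin and tumor response for each malignancy"; the second is "the relationship with tumor mutational frequency using whole exome sequencing and response", with nothing about disease. The same section gives their status: "Analysis of activity Cohorts B and the biomarker data will be primarily descriptive and exploratory".

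Section 10.3.2 offers log rank tests of mutational load against time-to-event outcomes in MCM and ALM, and does not say whether the cohorts are combined.

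**The concern.** CD8 infiltrate falls under both instructions: per disease in 10.2, all patients in 10.3.1. An analyst cannot follow both. For the other listed markers, 10.3.1 is the only instruction on tests against response, and it ignores cohort.

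The two cohorts are different diseases. Section 1.7 reports, for anti-PD-1 monotherapy, "objective response rate was 32%(15-54%) in ALM, and 23% (10-40%) in MCM respectively". Section 1.8.3 reports different candidate driver genes for the two. A marker that mainly separates MCM from ALM could therefore look related to response. A marker that works within each disease could also be obscured by the difference between them. The stated purpose of these analyses is to refine which patients should receive the combination, and both errors work against that.

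**Working it through.** **Inputs from the documents.** Section 10.2: "49 patients with MCM (cohort A) will need to be enrolled into this study", and 24 ALM patients. The MCM figure reproduces. With n = 39 and success at 14 or more responses, the exact one-sided error at 25% is 0.086 and the power at 45% is 0.905; 39/(1 − 0.20) = 48.75, so 49. Response rates: 23% MCM and 32% ALM (section 1.7), and the 45% design alternative for MCM (section 10.2). The plan states no size, level or power for the marker tests, so there is no figure of its own to reproduce for them.

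**Assumptions.** Two-sided 5% level; normally distributed marker with SD 1 within cohort; ALM mean shifted by 0 to 1.5 SD. An ALM rate of 25% or 45% is also assumed where used below.

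**Why pooling matters.** With no marker effect inside either cohort, the expected difference between responders and non-responders is the shift multiplied by the difference in their ALM shares.

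- At 23%/32%: ALM share of responders = 24×0.32/(49×0.23 + 24×0.32) = 7.68/18.95 = 0.405. Share of non-responders = 16.32/54.05 = 0.302. The spurious difference is 0.10 SD per SD of shift.
- At 45%/25%: 6/28.05 = 0.214 against 18/44.95 = 0.400. The spurious difference is −0.19 SD per SD of shift.
- At equal response rates the shares are equal and the spurious difference is zero.

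The shift also widens the pooled spread, by a factor √(1 + p(1−p)δ²) with p the ALM share and δ the shift. A true 0.8 SD effect at 23%/32% with the marker 1 SD lower in ALM becomes (0.80 − 0.10)/1.11 ≈ 0.63 SD.

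**Simulation.** 8,000 trials per setting, 49 + 24 patients. The pooled Wilcoxon test was compared with the van Elteren test, which takes the responders' rank sum within each cohort, weights it by 1/(n_h + 1), sums and standardises.

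False-positive rate with no association within cohort (pooled / stratified):

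| ORR MCM/ALM | 0.5 SD shift | 1 SD | 1.5 SD |
|---|---|---|---|
| 45/45 | 4.9% / 4.9% | 5.0% / 5.1% | 5.6% / 5.7% |
| 23/32 | 5.5% / 5.3% | 6.9% / 5.2% | 7.6% / 4.7% |
| 45/25 | 6.1% / 4.9% | 10.9% / 5.3% | 15.2% / 5.2% |

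With 39 + 19 patients (24 × 0.8 ≈ 19, applying the 20% loss to ALM too), the 23/32 pooled row is 5.3%, 6.1% and 7.0%.

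Power for a true 0.8 SD within-cohort effect (pooled / stratified):

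| ORR MCM/ALM | No shift | 1 SD shift |
|---|---|---|
| 23/32 | 81.0% / 79.3% | 60.1% / 79.6% (marker lower in ALM) |
| 45/25 | 88.2% / 86.2% | 59.4% / 86.3% (marker higher in ALM) |
| 45/45 | 90.1% / 89.2% | 82.9% / 88.7% (marker higher in ALM) |

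When the shift runs the other way, the pooled test rejects more often (94.8% against 86.9% at 45/25). That is the same bias pointing in a favourable direction, not a gain in efficiency.

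**Categorical markers.** Take prevalence 10% in MCM and 36% in ALM, the low MCM figure and the ALM figure for KIT in sections 1.2 and 1.3. At 23/32 the expected pooled counts are 3.89 and 15.06 (responders with and without the marker) and 9.65 and 44.40 (non-responders). The odds ratio is 3.89×44.40/(15.06×9.65) = 1.19 with no within-cohort association. Fisher's test rejects in 4.3% of trials at 23/32 and 5.4% at 45/25. A much wider prevalence gap (20% against 70%, assumed) gives 9.8% at 45/25.

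**The case against.** The strongest reply is that pooling is inferred. The phrase in 10.3.1 names a population, the tests stand in a separate paragraph, and cohort-aware wording appears elsewhere (the response rate in 10.3.1, CD8 in 10.2, the circulating markers in 9.3.1). That stands in part: it would be wrong to say that the whole plan pools its biomarker tests. For CD8 the defect is a conflict between two sections; for the rest it is missing cohort handling. But unstratified tests in all enrolled patients, named directly after a by-cohort response rate, are most naturally read as combined.

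A reader might infer that cohort confounds every marker comparison. The documents do not support this. False associations need both the response rate and the marker to differ by cohort. The 32% and 23% carry wide, overlapping intervals and come from monotherapy. Sections 1.8.2 and 1.8.5 describe low mutational burden for both diseases together. No cohort distributions are given for the continuous markers. The KIT figures are not like for like: 36% counts any aberration, and section 1.4 says activating mutations are much less common in ALM.

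It is also fair that the larger false-positive rates come from response gaps wider than, and opposite in direction to, the protocol's own figures. They show sensitivity, not an expected size.

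Finally, the analyses are labelled exploratory and have no stated level. That limits the consequence, but it does not excuse a bias that is easy to remove, and the mutation-response relationship is listed as a secondary objective in sections 2.0 and 10.1.

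**Conclusion.** The point holds for section 10.3.1 and is of modest size. The section conflicts with 10.2 on CD8 and leaves cohort out of the tests for the other markers.

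For continuous markers, false-positive inflation at the protocol's own response rates is small: 5.5% to 7.6% for shifts of 0.5 to 1.5 SD. It reaches about 11% to 15% only with an assumed 45%/25% split and shifts of 1 to 1.5 SD. Loss of power is the larger risk: about 60% instead of 80% under an opposing 1 SD shift at 23%/32%, and some loss (83% against 89%) even with equal response rates. For categorical markers with KIT-like prevalence the inflation is negligible.

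These sizes rest on assumed shifts, normal markers and an assumed two-sided 5% level. A reader might infer that the trial's main result is at risk; it is not, because the primary test uses MCM patients alone.

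**What to change.** In section 10.3.1, report each marker-response comparison separately for MCM and ALM. For any combined analysis, replace the named tests with cohort-stratified ones: van Elteren for continuous factors and an exact stratified Cochran-Mantel-Haenszel test for categorical factors. In section 10.3.2, stratify the log rank tests by cohort if the cohorts are combined. Make the CD8 wording in 10.3.1 agree with the per-disease definition in 10.2.

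The cost is wording and a few lines of code. For continuous markers, stratifying loses about 1 to 2 points of power when the marker does not differ by cohort (90.1% to 89.2% at 45/45; 81.0% to 79.3% at 23/32; 88.2% to 86.2% at 45/25). The power cost of moving from Fisher to the exact stratified test was not calculated. Stratified tests look for a common effect and can miss effects that run in opposite directions in the two diseases; the by-cohort results are needed to show those.

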### 1.8.2 Mutational Burden in Metastatic Melanoma

Malignant melanoma contains the highest prevalence of somatic mutation per megabase, especially high base-pair mutation rate attributable to UV exposure, in comparison to other cancers. The highly variable prevalence of somatic mutations among each cancer genome, between 0.001 per megabase (Mb) to more than 400 per Mb, is likely contributed by known mutagenic exposure, mismatch repair machinery defects, or the duration of cellular damage/replication error of passenger mutations between the fertilized egg to the time of samples analysis in cancers arise from self-renewing tissues (37, 38).

High mutational burden correlated with overall survival in patients with cutaneous melanoma treated with ipilimumab (39) or lung cancer treated with anti-PD1 (40).

[figure not shown]

Figure 1 Mutational Landscape of Tumors According to Clinical Benefit from Ipilimumab Treatment. Panel A shows the mutational load (number of nonsynonymous mutations per exome) in the discovery and validation sets, according to status with respect to a clinical benefit from therapy. Panel B depicts the Kaplan-Meier curves for overall survival in the discovery set for patients with more than 100 nonsynonymous coding mutations per exome and patients with 100 or fewer mutations(39).

Although the predictive markers research and discovery in cutaneous melanoma has made great progress, there is a paucity of data on the biomarkers predictive of response in patients with MCM and ALM receiving checkpoint inhibitor therapy and very little data in any patient population receiving combination CTLA4 and anti-PD1 inhibitor therapy. Furney et.al observed an average of twelve to sixty-six non-synonymous single nucleotide variants (SNV) in whole exome sequencing of both MCM and ALM (41, 42), at least 5-10 fold less mutational load than typically seen in cutaneous melanomas. Paucity of data from next-generation whole genome/exome sequencing in MCM and ALM, with less than 10 study subjects from each disease, limits analytical power and is subjected to ascertainment bias.

A preliminary study on whole exome sequencing of anorectal, nasopharyngeal and vulvovaginal MCM demonstrated unique mutational pattern between MCM and cutaneous melanoma. Additionally, analysis of each MCM subgroup could also distinguish each subset of MCM by different mutational profiles (Gorden et al; SMR 2015)

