#### 1.8.5 Tumor's Neoantigen Epitopes Discovery in Metastatic Melanoma

Because antigen presentation via MHC class I molecule as well as cytotoxic T-cell recognition

and binding is essential for immune checkpoint inhibitors to function, computational analyses from whole exome sequencing have generated putative mutant and non-mutant peptides from each non-synonymous missense mutation. An algorhythmic computational method was able to predict that the somatic neoantigen epitope formed from mutant peptides, bound patient-specific MHC class 1 molecules with higher affinity ( $\leq 500\text{nM}$ ) and strength.

Further, a number of immunogenic peptides were discovered among patients who achieved long-term clinical benefit. The number of 9- to 10- amino acid immunogenic neoantigens with ( $\leq 500\text{nM}$  binding affinity for HLA class I molecules (using patient-specific nonsynonymous mutation and HLA types) are also associated with clinical benefit to CTLA-4 monoclonal antibody therapy(39, 48). Interestingly, while both neoantigen loads and mutational burden are independently correlated with clinical benefit to CTLA-4 monoclonal antibody, both mutational load and neoantigen load were strongly correlated to each other (Spearman rho = 0.97,  $p < 0.001$ ) (48). Although prior study proposed a panel of shared neoantigen peptides among subjects with long-term clinical benefit from CTLA-4 monoclonal antibody (39), subsequent studies failed to identify recurrent or shared neoantigens or neoantigen epitopes that could predict response to CTLA-4 monoclonal antibody therapy. Instead, majority of neoantigen epitopes identified through exome sequencing appears to be private events without obvious shared recurrent domains among responders (48).

Based on preliminary analysis of low mutational burden in MCM And ALM, it is important to assess whether MCM and ALM low mutational burden translate into low number of neoantigen loads, and whether predicted neoantigen peptides burden in variant melanomas have any clinically meaningful association with clinical benefits to combined immune-checkpoint inhibitor therapy or not.

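### Section 10.3.1 enters the neoantigen marker as an undefined yes/no presence, although the protocol's rationale concerns the number of predicted neoantigens; the count would be the better variable at no cost

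*Combined protocol and SAP*

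**What the plan says.** Section 10.3.1 introduces the biomarker work by saying that "additional hypothesis-generating analyses will be undertaken to explore whether somatic mutational loads" and a list of other features might be associated with response. Several listed features are graded, such as mutational load and the level of CD8+ infiltrate. The neoantigen feature appears as "presence of tumor specific neoantigen, TCR clonality, gene expression profiles". On testing, the section says: "Categorical factors and continuous factors will be compared between responders and non-responders using Fisher's exact tests and two-sample Wilcoxon rank sum test respectively".

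The rationale uses a different quantity. Section 1.8.5 reports that the number of 9- to 10-mer predicted neoantigens with affinity at or below 500 nM was associated with benefit from CTLA-4 blockade. It says that the "majority of neoantigen epitopes identified through exome sequencing appears to be private events without obvious shared recurrent domains among responders". It then sets this trial's question as "whether predicted neoantigen peptides burden in variant melanomas have any clinically meaningful association" with benefit from the combination.

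Objective 2.6 and section 9.2.5 speak of candidate epitopes and their predicted binding affinity. No section defines a patient-level neoantigen variable or says when a tumor counts as positive.

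**The concern.** A presence factor is categorical, so under the section's own rule it would go to Fisher's exact test. Such a test can separate responders from non-responders only if a fair number of tumors fall on each side of the split. Both natural readings of presence are doubtful on that score: a given epitope may be carried by one patient only, and some predicted epitope may be found in almost every tumor. In either case the count, which the pipeline yields anyway, would be thrown away.

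Because no positivity rule is written down and sequencing is batched at the end of the study (section 9.2.2), a cut-off could also be settled after responses are known. At stake is how much one exploratory analysis can tell; no trial decision depends on it.

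**Working it through.** **The plan's own sample size.** Section 10.2 gives 39 evaluable MCM patients, 25% against 45%, one-sided 10%, 90% power, exact binomial. With success declared at 14 or more responses of 39, the exact type I error is 0.0862 and the power 0.9048. Allowing for 20% dropout, 39/0.8 = 48.75, so 49. These figures reproduce. The documents give no sample size, power or expected prevalence for the neoantigen marker.

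**Inputs.**
- Population: 10.3.1 says all enrolled patients, so 49 + 24 = 73. I also show 39 (evaluable MCM) and 63 (39 + 24).
- Responders: 45% is the design alternative for MCM. Applying it throughout is an assumption, giving 18 of 39, 28 of 63 and 33 of 73.
- Variants: section 1.8.2 says that a cited study "observed an average of twelve to sixty-six non-synonymous single nucleotide variants (SNV) in whole exome sequencing of both MCM and ALM". These are averages, and the same section warns that such sequencing data, "with less than 10 study subjects from each disease, limits analytical power and is subjected to ascertainment bias".
- Binders per variant, b: not in the documents. Assumed range 0.05 to 0.5.
- Two-sided 0.05 is my yardstick; the plan sets no level for the biomarkers.

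**Reading 1: a specific epitope.** If one patient carries it, the smallest two-sided Fisher p arises when that patient is a responder, and equals responders/N: 18/39 = 0.46, 28/63 = 0.44, 33/73 = 0.45. No binder rate is needed here.

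**Reading 2: any predicted epitope.** If tumors have similar counts, P(negative) = exp(-m x b) for m variants.

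| b | m = 12 | m = 66 |
|---|---|---|
| 0.05 | exp(-0.6) = 55% | exp(-3.3) = 3.7% |
| 0.1 | exp(-1.2) = 30% | exp(-6.6) = 0.1% |
| 0.25 | exp(-3) = 5% | about 0 |
| 0.5 | exp(-6) = 0.2% | about 0 |

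If counts vary between tumors (negative binomial, shape 2, assumed), P(negative) = (1 + m x b/2)^-2. At m = 12, b = 0.25 this is 2.5^-2 = 16%; at m = 66, b = 0.05 it is 2.65^-2 = 14%. Variation between tumors therefore produces more negatives.

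**How many negatives Fisher needs.** Take the direction that 1.8.5 suggests, with every negative tumor a non-responder:

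| Negatives | N = 39 | N = 63 | N = 73 |
|---|---|---|---|
| 3 | 0.235 | 0.247 | 0.247 |
| 5 | 0.0502 | 0.060 | 0.060 |
| 6 | 0.022 | 0.029 | 0.029 |

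So at least six negatives are needed, none of them responding. At a 25% response rate the requirement rises to 10 of 39 (with 10 responders, p = 0.040) or 12 of 73 (with 18 responders, p = 0.031).

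**Can presence still work?** Yes. At b = 0.1 and m = 12, about 0.30 x 73 = 22 tumors are negative. If 5 of those 22 respond against 28 of 51 positives, Fisher p = 0.020. At N = 63, 4 of 19 against 24 of 44 gives p = 0.026.

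**Presence against count.** Simulation with 2000 runs, N = 73 and mutation counts negative binomial with shape 2. Response probability rises from 15% to 75% with mutation-count rank (mean 45%). Each variant yields a binder with probability q. All of these settings are assumptions.
- Mean 66, q = 0.2: 98% positive; power about 0.1% for presence and 83% for the count.
- Mean 12, q = 0.2: 79% positive; about 29% against 63%.
- Mean 12, q = 0.05: 41% positive; about 22% against 29%.

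The count does better in each case, but the advantage shrinks when binders are rare.

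**The case against.** A reader might infer that, on the protocol's own figures, nearly every tumor will be positive and the test cannot show anything. The documents do not support that. They give variant averages but no binder rate, and the averages come from very small series. At the low end of the variant range with few binders per variant, presence splits the sample usefully. An expression filter would add negatives: section 1.8.6 says that many neoantigens predicted from exome data are expressed at negligible levels, and section 9.2.4 plans RNA sequencing.

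A reader might also infer that objective 2.6 is bound to return a null result. It is not. The objective concerns binding affinity, section 9.2.5 produces affinities in silico, and 10.3.1 already offers a rank-sum test for continuous factors. Nothing assigns the neoantigen marker to Fisher's test by name; that follows only from the word presence in a prose list.

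Two further points stand. Section 1.8.5 reports a Spearman correlation of 0.97 between neoantigen load and mutational load in earlier data, so the count may add little to the mutational load already in the list. And section 10.2 calls the biomarker analyses primarily descriptive and exploratory. These points limit the claim and its priority. They do not explain why the analysis section names a different quantity from the rationale.

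**Conclusion.** The point holds in a limited form: section 10.3.1 names a yes/no variable without a definition, while section 1.8.5 asks about burden and cites the number of binders.

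For a specific private epitope, presence is uninformative (smallest p about 0.45), and this rests only on the protocol's statement that most epitopes are private and on the assumed 45% response rate. For any predicted epitope, the conclusion depends on a binder rate that the documents lack. Near 66 variants about 96% or more of tumors would be positive at 0.05 or more binders per variant, if counts are similar. Near 12 variants and 0.05 to 0.1 binders per variant, about 30-55% could be negative, which leaves a test that is weak and discards count information but can still reach significance.

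The primary endpoint, the sample size and the trial's decision rule are unaffected. This is a free improvement of low priority.

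**What to change.** In section 10.3.1, replace the presence factor with neoantigen load: the number of predicted binders at or below 500 nM per tumor, taken from the section 9.2.5 pipeline. State whether an expression filter from the RNA data applies. Compare load between responders and non-responders with the Wilcoxon rank-sum test already planned, and interpret it beside mutational load because of the 0.97 correlation cited in section 1.8.5.

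The cost is a sentence or two of text, settled before the batched sequencing results are available. It needs no new assay, sample or patient: section 9.2.5 already produces the candidate epitopes and affinities, and the count is a tally of them.
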